9.2.3 Evaluation and Management

Investigators will follow participants who have developed SAEs during the study until the event has resolved, stabilized, subsided, disappeared, is otherwise explained or the participant is lost to follow-up. Treatment of the SAE is at the sole discretion of the site investigator and according to good medical practice.

10.0 PARTICIPANT RECRUITMENT AND WITHDRAWALS

1. Recruitment

We will recruit and enroll WLWH over a 36-month period starting in January 2023. Recruitment will be at our 10 sites of HIV and/or reproductive care, when WLWH attend for routine care, in collaboration with their healthcare providers. Due to the high frequency of standard clinical HIV care visits, we anticipate that all participants can be recruited during clinic attendance for routine visits.

2. Participant Compliance

In our precursor study of 4vHPV vaccination, 90% of WLWH completed the 3-dose vaccination schedule. As we are recruiting from sites of HIV/reproductive care, these women are generally engaged in care and accustomed to frequent clinical visits that include procedures such as blood draws. Engagement with WLWH confirms their desire to have

their clinical questions answered through appropriate research. Moreover, this vaccine is not publicly funded in all provinces for older women so trial participation provides enhanced access to vaccine.

3. **Rate of Loss to Follow Up**

In our sample size calculation, we have allowed for 10% loss to follow-up between enrolment and primary outcome (month 7 serology). This is conservative and based on 10% attrition/year in our precursor study.

4. **Withdrawals**

Investigators or their delegates will attempt to contact those study participants who do not return for study visits. Study personnel will make at least three attempts to contact the participant using various communication means. Each attempt should be documented in the participant source documents.

A participant completing all visits up to and including the Month 24 visit will be considered to have completed the study.

Withdrawals will not be replaced. All withdrawals will be documented including the date of the withdrawal and the reason.

11.0 **TRANSPORTATION OF LABORATORY SAMPLES**

All shipments of serum samples are to be shipped frozen and prepared by qualified individuals ensuring that all shipments are packed and shipped according to IATA regulations and are to be packed using dry ice.

All shipments of HPV DNA testing aliquots are to be shipped frozen and prepared by qualified individuals ensuring that all shipments are packed and shipped according to IATA regulations.

All samples are to be clearly labeled with participant's 5-digit PID#, date of collection, and visit month.

All shipments must have an accompanying biological shipment listing, with a copy being retained at the site. A biological shipment listing template will be provided to the sites by the Study Coordinating Centre.

Prior to the shipment of any samples, the sites must inform the Study Coordinating Centre regarding the date of shipment to ensure that there is someone at the Coordinating Laboratory to receive the shipment. Confirmation must be received from the Study Coordinating Centre prior to the shipment of any samples. Sites should plan to ship Monday through Wednesday to ensure that samples arrive within 72 hours of packaging to ensure that thawing does not occur before processing.

The Coordinating Centre will arrange for shipment of all samples (serum, vaginal swabs) to the individual laboratories performing the analysis/testing.

12.0 LABORATORY METHODS AND ANALYSES

1. Antibody testing at Merck Laboratories

In order to attain comparability to licensure trial serologic results and comparable studies in immunocompetent persons, antibody assays will be conducted by our collaborator at Merck Laboratories, Q2 Solutions LLC, [name].

Each serum sample will be divided into 2 aliquots: #1 will go to the Merck laboratory for in-house serotesting and #2 will go to the BC Women's Research Lab (Women's Health Research Institute) for storage. Serum anti-HPV6, 11, 16, 18, 31, 33, 45, 52, and 58 immunoglobulin levels will be measured using competitive Luminex immunoassay (cLIA), and reported in arbitrary units (milli-Merck Units per ml [mMU/ml]) relative to the standard curves generated for each HPV type. Antibody titers are determined in a competitive format where type-specific labeled neutralizing antibodies for each type compete with patient serum antibodies for binding to conformation-sensitive neutralizing epitopes on virus like particles. Seropositivity is defined as > 50 mMU/ml for HPV6, 29 mMU/ml for HPV11, 41 mMU/ml for HPV16, 59 mMU/ml for HPV18, 29 mMU/ml for HPV31, 22 mMU/ml for HPV33, 15 mMU/ml for HPV45, 20 mMU/ml for HPV52, and 15 mMU/ml for HPV58.³⁶

2. HPV DNA Testing using Self-Collected Vaginal Swabs

All DNA testing for HPV will use vaginal swabs in STM vials. Swabs will be tested by [name] at the National Microbiology Laboratory, [name], using a commercially available research assay for the detection of high and low risk HPV genotypes.

We are utilizing a research HPV DNA assay not a clinical HPV assay, and we won't have the test results back in a timely manner as these will be run in batches, maybe 12-24 months after collection, possibly even more. The sensitivity and specificity of this test is not adequate for actionable results. The importance of participating in available clinical screening will be reinforced with participants during the course of study participation.

In cases where the same high risk HPV DNA type is found on 2 occasions, a minimum of 6 months apart, primary care providers will be notified and recommended to follow up with pap or HPV testing, or colposcopy.

3. Use of Retention Self-Collected Vaginal Swabs

The primary purpose of the second swabs, which are collected at 5 of the study visits, is as a retention swab. This swab will be used in the event that the primary swab has inadequate sample or is otherwise compromised. If these swabs are not needed for this purpose, we may test these samples for bacteria that are commonly found in the vagina, and the vaginal samples and blood for a series of viruses that are very common in humans and can be in the body for a long time with no symptoms if the immune system is healthy. We will test for herpes simplex virus or HSV, mononucleosis as well as cytomegalovirus. This testing may include antibody testing and viral DNA and viral RNA testing.

13.0 STATISTICAL ANALYSIS

1. Statistical Analysis Plan

All primary analyses will be performed based on modified intention to treat (mITT). Data missing more than 5% will be imputed using multiple imputation by chained equations to avoid bias.⁴⁴ All variables that will be included in analytic models, including all outcome and HPV related variables, with the addition of important demographic variables will be included in imputation equations as advised in the literature.⁴⁵

2. Demographics

Characteristics of the full study population will be described using counts and proportions for categorical variables, means and standard deviations for normally distributed continuous variables, and medians and interquartile ranges for skewed continuous variables. Sex is integral to this project as eligible people must have a cervix, which is biologically only present when female at birth, as we aim to inform the use of the 9vHPV vaccine in individuals with uterine cervixes. Gender is also very relevant given that non-binary females and trans men may be included. We will capture self-identified gender through our demographics questionnaire, and examine differences by gender.

3. Primary Analysis

To determine if 2 doses of 9vHPV vaccine are non-inferior to 3 doses in WLWH, we will evaluate serologic response by comparing peak anti-HPV16/18 GMTs individually with 95% CI at 7 months in both groups using linear regression, adjusted for HIV viral load, CD4+ T cell count, and age.⁴⁶ We will similarly compare seroconversion rates in the two groups using logistic regression. Adjusting for age and HIV clinical parameters instead of stratifying by them (they are also unlikely to be importantly imbalanced in a trial this size) can improve sensitivity/power.⁴⁶ Using immunobridging,^{47,48} we will also compare the rate of seroconversion and peak anti-HPV GMTs to previously published two-dose 4vHPV responses in girls and women without HIV²³ and previously published three-dose 9vHPV responses in girls and women without HIV using logistic regression for seroconversion rates and one-sample t-tests for GMT comparisons.^{18,49} Immunobridging is a highly accepted method of evaluating HPV vaccines in different groups when a correlate of protection is unknown and efficacy endpoints such as cervical dysplasia take many years to develop. Level of antibody response after two doses will be described by clinical and demographic variables (age, CD4 count, HIV viral load, HPV DNA or antibody positivity at baseline, and lifetime number of sexual partners) using general linear models.

4. Secondary Analyses

1. To compare differences in antibody persistence, longitudinal GMTs will be compared between the two groups (routine vs. extended dosing interval) to determine if there are differences in the rates of antibody persistence at month 24. We will use mixed-effects linear regression on the log-transformed titers to estimate the rate of decline of antibody titers by time since first vaccine dose. Differences in rates will be compared directly using an interaction term between group and time.

2. To evaluate HPV self-sampling acceptability, quantitative survey results will be summarized as frequencies. Comparisons among subgroups (e.g. by age, region, cultural background, and gender) will be conducted using linear regressions.

5. Exploratory Analyses

1. To determine if 2 doses of 9vHPV vaccine are non-inferior to 3 doses in WLWH for the additional 9vHPV types not in the primary outcome, we will evaluate serologic response by comparing peak anti- HPV6/11/31/33/45/52/58 GMTs individually and seroconversion rates with 95% CI at 7 months in both groups using linear and logistic regression, respectively, adjusted for HIV viral load, CD4+ T cell count, and age.
2. As the world is moving towards one-dose HPV vaccine schedules, we will take the opportunity to collect preliminary data on the peak one-dose antibody response at month 1. These data will inform the sample size calculation for a future one-dose trial, as appropriate, and will be reported as anti-HPV16/18 GMTs with 95% CI.
3. To evaluate significant adverse events, the proportion (and 95%CI) of participants who experience significant adverse events will be calculated for the entire study population, and also by group. The types and severities of adverse events will be described.
4. To address vaccine efficacy, we will calculate incidence rates of abnormal cervical cytology and histology (HSIL), and breakthrough persistent HPV infection. HSIL will be described with Kaplan-Meier curves. If sufficient numbers of each are observed, Kaplan-Meier curves will be calculated by age range (21-30, 31-39, 40-55, >55), CD4 count (<200, 200-500, >500), HIV viral load (detectable vs. undetectable), and prior HPV status. Persistent HPV will be described by type of HPV, high vs. low-risk, and vaccine type or not, using Kaplan-Meier curves for HPV acquisition and frequencies and percentage for persistent infections. Given the capability to intervene with early pre-cancerous changes in the cervix, we cannot ethically use cervical cancer as an end point but other efficacy endpoints are critical for an HPV vaccine study as an immune correlate of protection is unknown.
5. To assess the uptake of HPV vaccination of WLWH, a screening log will be kept by each study site to track how many WLWH aged 18-45 were not eligible to participate in the study due to having already received an HPV vaccine. The proportion of women who were previously vaccinated will be calculated for the population of women aged 18-45 at each site and across the country.

6. **Planned Subgroup Analyses**

Subgroup analyses by gender (woman, gender-diverse) will be conducted if sample size allows, examining differences in all outcomes by gender. Primary and secondary analyses will be analyzed by clinical and demographic variables including: age, ethnicity, region, CD4+ T cell count, HIV viral load suppression (vs. unsuppressed), and HPV DNA or anti-HPV antibody positivity at baseline.

7. **Sample Size Calculations**

The sample size was calculated based on the primary evaluation of non-inferiority of the immunologic response to 2 vs. 3 doses of 9vHPV vaccine. For ethical reasons, all 2 dose recipients will eventually receive a third dose but we used a dose ranging study design to achieve this end. Using a one-sided alpha = 0.025, a non-inferiority margin of 0.5 based on benchmarks set by Merck for other immunobridging studies leading to licensure,⁴³ a standard deviation of 1.379 calculated from HPV16 GMTs in our prior cohort of WLWH, and 80% power, we would require 205 participants per group (total: 410). Given an anticipated dose completion rate of 90% based on our prior experience, we aim to recruit 225 participants per group to achieve power to detect non-inferiority in peak 2 vs. 3 dose GMT.

At 6 of our 10 sites, there are >900 WLWH who are unvaccinated and eligible for this study, suggesting there are likely ~1800 eligible women at all sites. We therefore anticipate being able to achieve the target sample size of 450 given that 90% of eligible WLWH screened in our precursor study were enrolled.

14.0 **DATA MANAGEMENT**

The data safety and monitoring committee (DSMC) will be coordinated through established processes by the CTN and will function at pre-specified intervals to monitor the conduct and progress of the trial, evaluate the accumulating study data including all serious adverse events, recommend protocol changes, alert trial leaders to emerging procedural or ethical issues, and monitor enrolment to ensure timely conduct of the trial. All up to date adverse events will be reported to the DSMC at each meeting to ensure participant safety. All other data including immunogenicity, efficacy, and self-sampling acceptability will be reported to the DSMC as it becomes available throughout the study for assessment of study conduct and progress. Reports from the data management process will be provided to the DSMC to ensure data quality.

Source document data will be transferred to a case report form by study personnel at the investigative sites. The participant identification number (PID) will be assigned to each participant and used to label the case report form and all study samples. Data will be entered through a direct-entry process and managed on Research Electronic Data Capture (REDCap) software.

Data will be entered into a relational database with pre-programmed quality assurance checks. Queries will be resolved with the site study coordinator, with appropriate documentation. Backup copies of the database will be made daily and stored securely at a second location. No personal identifiers will be included in the database. Analysis will be conducted using statistical software (e.g. SAS, SPSS, or R).

All personal information pertaining to participants will be securely stored at sites in a locked room, under the supervision of the site study coordinator(s) and accessible to study staff only. Where

electronic databases are used as mechanisms for participant tracking etc. these databases will be password protected and available only to specified study staff and site investigators.

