With HIV seropositivity rates in some countries at ~25% and many countries with >1 million people living with HIV, the ability to reduce the vaccination schedule by 1 dose could have a substantial positive impact on program feasibility. For more countries to be able to adopt HPV vaccination programs, costs associated with such programs must be reduced. Hence, data to determine the immunogenicity and effectiveness of reduced dosing will inform Canadian and global public health recommendations as well as potentially provide support for reduced dose programming in high HIV seroprevalence low and middle-income countries, thereby accelerating global health equity.

The extended dosing interval allows us to assess peak antibody titers to 3 doses in the routine group at month 7 and peak antibody titers to 2 doses in the extended group at month 7, while still offering the current 3-dose standard of care to all WLWH in the study. It is standard in vaccine research to use the “peak” antibody titer (i.e., titer at 1 month post vaccination) as a primary immunologic endpoint demonstrating overall maximal immunologic response. This endpoint is also the basis of licensure for many vaccines and would be necessary and sufficient for regulators to change the recommended use of a vaccine. Indeed, the approval of reduced 2 dose HPV vaccine schedules in the general population was based on immunobridging data of the peak antibody titers.^{23, 24}

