3.0 OBJECTIVES

The overall goal of the study is to assess whether 2 doses of vaccine are non-inferior to 3 doses. Participants will be randomized 1:1 to receive 3 doses of 9vHPV vaccine at the routine vaccine schedule of 0/2/6 months or at an extended schedule of 0/6/12 months.

1. **Primary Objective**
 - 1) Determine whether peak anti-HPV16/18 geometric mean titers (GMTs) to 2 doses of 9vHPV vaccine are non-inferior to peak anti-HPV16/18 GMTs to 3 doses at month 7.
2. **Secondary Objectives**
 - 2) Compare the antibody persistence at month 24 between the routine and extended vaccine schedule.
 - 3) Elucidate the acceptability of HPV self-sampling among WLWH in Canada.

3. Exploratory Objectives

- 4) Determine whether peak anti-HPV6/11/31/33/45/52/58 GMTs from 2 doses of 9vHPV vaccine are non-inferior to those from 3 doses at month 7.
- 5) Assess peak anti-HPV16/18 GMTs to 1 dose at month 1.
- 6) Describe the incidence, type, and severity of adverse events in WLWH.
- 7) Elucidate the efficacy of 9vHPV vaccination up to month 24 (via persistent HPV infection with 9vHPV types, and cytological and histological HSIL).
- 8) Engage in a BC Cancer Registry linkage to investigate rates of pre-cancer or cancer diagnoses.
- 9) Investigate the role of viral and bacterial co-infection in the development of cervical dysplasia and vaccine breakthrough HPV infection in WLWH
- 10) Assess the uptake of HPV vaccination in WLWH aged 18-45 across Canada prior to study.

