7.2.1 Suspension of Study Procedures in Pregnancy

In the event of a pregnancy during the study, the investigative site is to notify [name] at the Study Coordinating Centre using a pregnancy reporting form as soon as the investigative site is made aware of the pregnancy. Following the resolution of the pregnancy, the investigative site will provide an update to the Pregnancy Reporting Form and inform the Study Coordinating Centre.

Study vaccination is to be suspended in pregnant participants and may be resumed at the resolution of pregnancy. All other study procedures may continue.

If a participant has a positive pregnancy test as part of the study visit, the clinic doctors or nurses will be notified and they will let the participant know about the result. If the participant receives a positive test outside of the clinic, they are asked to let the team know. Following the diagnosis of pregnancy, study vaccination will be temporarily stopped, and participants will be invited to resume vaccination at the same point that it was stopped, 1 month after the conclusion of the pregnancy if they choose to do so.

Pregnant participants will be invited to sign a Pregnancy Consent Form.

Information to be collected following signing of the Pregnancy Consent includes:

- estimated date of delivery
- the outcome and mode of delivery
- any important diagnoses associated with the pregnancy and delivery
- the date of birth or pregnancy loss
- the gestational weeks at birth or pregnancy loss
- infant's sex and weight
- infant's APGAR scores

- if the infant was required to stay in hospital longer than usual, and if so, what the cause was

3. Summary of Study Visits

Table 1A. Schedule of Visits (Routine Group: Follows Routine Vaccine Schedule)

	Informed Consent	Pregnancy Test	9vHPV Vaccine	Blood Draw	HPV DNA Swab ^a	AE Assessment	Ongoing Medical History	HPV Self-Sampling Questionnaire
Month 0	X	X	X	X ^c	X	X	X	X ^b
Month 1				X		X	X	
Month 2		X	X			X	X	
Month 6		X	X		X	X	X	
Month 7				X		X	X	
Month 12					X	X	X	
Month 24				X	X	X	X	X

^aSelf-sampling where acceptable to participant, ^b Pre-HPV-swabs, ^c Pre-vaccination

Table 1B. Schedule of Visits (Extended Group: Follows Extended Vaccine Schedule)

	Informed Consent	Pregnancy Test	9vHPV Vaccine	Blood Draw	HPV DNA Swab ^a	AE Assessment	Ongoing Medical History	HPV Self-Sampling Questionnaire
Month 0	X	X	X	X ^c	X	X	X	X ^b
Month 1				X		X	X	
Month 2								
Month 6		X	X	X ^c	X	X	X	
Month 7				X		X	X	
Month 12		X	X		X	X	X	

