7.4.2 Study Duration

The primary endpoint occurs at month 7 prior to completion of all doses in the extended interval group. All additional endpoints beyond month 7 are based on completion of the three doses and will provide critically-needed data on extended dosing intervals, HPV self-sampling acceptability, safety, and efficacy of 9vHPV vaccines in WLWH for whom the data is currently extremely limited. The 24-month follow-up duration will allow us to map immune titer dynamics to the vaccine out to the expected plateau in immunocompetent populations based on our prior data from WLWH (data not published) as well as the general population.^{34, 35}

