7.4.4.2 Indications for a Delay in Vaginal Swab Sampling

- Self-obtained samples may continue to be collected during pregnancy.

- Participants must not be menstruating at the time of the vaginal swabbing. The participant may have all other study procedures performed. The participant will be invited to take the swabs home to self-collect when they are not menstruating with instructions on how to return the swabs to the study centre.

7.4.4.3 **Indications for a Delay in Study Blood Sampling**

- Administration of immunoglobulins and/or any blood products within 30 days of study blood sampling
- Administration of any live virus vaccines given with 28 days of a blood sample
- Administration of inactivated or recombinant vaccines (e.g. Influenza, Hep B, Tdap, COVID) up to 8 days before study blood sample collection is acceptable

7.4.4.4 **Contraindication for Continuation of Study Procedures**

- Withdrawal from the study
- Anaphylactic reaction to HPV vaccine related component
- Development of any newly confirmed or suspected immunosuppressive or immunodeficient condition (other than HIV/AIDS)
- Administration of any HPV vaccine not provided as part of the study
- Investigator decides it is not in participant's best interest
- Participant decides to discontinue vaccine series

7.4.5 **Outline of Study Visits**

Month 0

At the Month 0 visit, the following will be done:

- Collection of informed consent.
- Baseline information will be recorded including information such as: general health history, HIV history and medication history, current antiretroviral medications
- A brief physical assessment (temperature, height, weight).
- Regular clinic and study bloodwork.
- A urine pregnancy test (regardless of age or sexual activity).
- A short questionnaire regarding how the participant feels about self-collecting a vaginal swab for the purpose of HPV screening for cervical cancer.
- A self-collected vaginal swab for detection of HPV DNA, and a retention swab.
- The first of three HPV vaccine doses will be given.
- Instructions regarding the 14-Day Post-Vaccine Symptom Diary

Month 1

At the month 1 visit the following will be done:

- Assess ongoing consent.
- Review of any changes in health status and/or medications.
- Review of all adverse events occurring in the first 14 days following vaccination and any significant adverse events following this period.
- Study bloodwork.

Month 2

This visit will only occur in participants in the routine group.

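### Section 7.4.4.4 ends blood sampling for a woman who chooses to stop the vaccine series, although the month-7 primary analysis by randomised group needs her sample

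*Protocol*

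**What the plan says.** **The question and its timing.** Section 3.0: "The overall goal of the study is to assess whether 2 doses of vaccine are non-inferior to 3 doses". Section 7.4.2: "The primary endpoint occurs at month 7 prior to completion of all doses in the extended interval group".

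**The analysis.** Section 13.1: "All primary analyses will be performed based on modified intention to treat (mITT"). The protocol does not define the modification. On gaps it adds: "Data missing more than 5% will be imputed using multiple imputation by chained equations to avoid bias".

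**The conduct rule.** Section 7.4.4.4 is headed "Contraindication for Continuation of Study Procedures", and one of its items is "Participant decides to discontinue vaccine series". The other items are study withdrawal, anaphylaxis, a new immunosuppressive condition, HPV vaccine from outside the study, and the investigator's judgement.

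**The pregnancy rule.** When vaccination is suspended for pregnancy, section 7.2.1 says: "All other study procedures may continue". Resuming vaccine afterwards is the woman's choice.

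**The expected shortfall.** Section 13.7 goes from 205 to 225 women per group on 90% dose completion. Section 10.3 describes the 10% allowance as loss to follow-up before the month-7 serology.

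**The concern.** An analysis by randomised group, even a modified one, needs the outcome from women who did not take all their doses. Section 7.4.4.4 appears to stop collecting it at the moment they stop vaccine, even when they are willing to attend. Women who stop may differ from those who continue in health, engagement in care and doses received, and all of these can bear on titre. Non-adherence, which could have been observed and analysed, would then become missing data in the primary comparison. A later analysis plan can choose how to model that gap, but it cannot recover blood that was never drawn.

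**Working it through.** **1. Does the rule reach the month-7 blood draw?**
- Section 7.4.4 deals in turn with vaccination (7.4.4.1), swabs (7.4.4.2), blood (7.4.4.3) and then continuation of procedures as a whole (7.4.4.4). Blood is therefore among the procedures that end.
- Withdrawal from the study is its own item, so choosing to stop vaccine is a different case with the same consequence.
- Sections 7.2.1 and 7.4.4.4 can meet in one woman. While her vaccination is suspended for pregnancy her samples may continue. If she then declines to resume, 7.4.4.4 ends them.

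**2. Who can be affected before month 7?** Doses fall at 0, 2 and 6 months (routine) and 0, 6 and 12 months (extended).
- In either arm a woman can stop after dose 1. In the routine arm she can also stop after the month-2 dose.
- In the extended arm, a woman who decides between months 6 and 7 not to have the third dose also meets the item. She has then had exactly the two doses the primary question concerns, and her month-7 sample is lost. The routine arm has no counterpart, since its series ends at month 6.
- The routes to missingness therefore differ by arm.

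**3. How many?** The plan's own figures:
- 450 × 0.10 = 45 women, or 22.5 per group, leaving 225 × 0.9 = 202.5 per group.
- 205 / 0.9 = 227.8, so 225 does not quite deliver 205 completers; 205 × 1.1 = 225.5 is closer.
- The 205 itself does not follow from the stated inputs: n = 2(1.96 + 0.84)² × 1.379² / margin² gives 63 per group for a margin of ln 2 and 120 for a margin of 0.5. That is a separate matter; 205 is used below only as a group size.
- The 45 is a ceiling. Section 10.3 counts the 10% as loss to follow-up, and an extended-arm woman who misses only dose 3 may decide so after month 7.

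**4. What does imputation do?**
- 5% of 450 is 22.5. Taken over the whole trial, 22 missing women (4.9%) would not trigger it and 23 (5.1%) would.
- Above the threshold, if the rule is followed, almost no woman who stopped has an observed month-7 titre. The model must borrow mainly from women who continued.

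**5. Illustrative size of the gap.** Assume that 5% of one arm is missing and left out, that their titres would have been half those of the rest, and that the SD of 1.379 is on the natural-log scale.
- The arm's observed mean log titre is too high by 0.05 × ln 2 = 0.035.
- SE of the group difference = 1.379 × √(2/205) = 0.136, so the shift is about a quarter of an SE.
- In the routine arm this works against non-inferiority; in the extended arm it works for it.

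**6. Illustration for women who stay in with fewer doses.** Take a true ratio of 0.5, the same SD and group size, and a fully compliant extended arm. A share q of routine-arm women carries two-dose titres.
- Shift = q × ln 2; type I error = 1 − Φ(1.96 − shift/0.136).
- q = 5%: shift 0.035, apparent ratio 0.518, type I error 4.4%.
- q = 10%: shift 0.069, apparent ratio 0.536, type I error 7.3%.
- The planned value is 2.5%. If the margin of 0.5 is read as a log difference, the figures are 3.8% and 5.6%.
- If instead 10% of both arms are one dose short, the apparent ratio is 0.5 × (2r)^0.1, where r is the one-dose to two-dose titre ratio. It runs from 0.475 (r = 0.3) to 0.517 (r = 0.7), so the direction is not fixed.

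**The case against.** The sponsor may say that 7.4.4.4 is meant to stop vaccine and not data collection, that few women will stop before month 7, and that imputation can use the baseline and month-1 titres. The first may be the intention, but the heading says otherwise and sites follow the text. The second may well be true and limits the size. The third is fair, but those titres do not show how a woman who stopped would have stood at month 7.

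A reader might go further and infer four things that the protocol does not support.
- *The claim rests on mITT alone.* The analysis plan is not at hand, the modification is undefined, and section 13.1 does not exclude a supportive per-protocol analysis. The 90% dose-completion basis in 13.7 even hints at a completer set.
- *Women with late doses are bled at calendar month 7, too soon for a peak.* No section says so. Section 1.0 ties peak to "titer at 1 month post vaccination", and the permission in 7.2.1 covers pregnancy only.
- *Type I error is inflated to 7.3%.* That needs a fully compliant extended arm, an assumed log scale, and 10% of the routine arm both one dose short and still sampled. The same 10% cannot also be the women lost under 7.4.4.4.
- *Month-24 samples are lost to an intention-to-treat analysis.* Section 13.1 applies mITT to the primary analyses, and section 7.4.2 bases later endpoints on completion of three doses.

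**Conclusion.** The point holds as a fault in a conduct rule. Followed as written, section 7.4.4.4 discards month-7 serum from willing women whom the primary analysis needs, while 7.2.1 keeps sampling women whose vaccination is suspended. The missing data are avoidable, may be informative, and can arise differently in the two arms. The number before month 7 is unknown and at most about 45 of 450. The direction of any bias cannot be told in advance, and the illustrative shifts rest on assumed titres and an assumed log scale. The lack of a named per-protocol analysis is a supporting matter to confirm with the sponsor, not an established omission. The change is worth making because it is cheap and because samples not taken cannot be recovered at analysis.

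**What to change.** - **Reconcile sections 7.2.1 and 7.4.4.4.** For the item on the participant's own decision to stop the series, and only that item, separate the end of study vaccine from the end of data collection. Say that she is still asked for the month-7 blood and the other samples already scheduled, unless she withdraws consent. The other items, and who is vaccinated and when, stay as they are.
- **Record the two events separately.** Note the date and reason for stopping vaccine apart from those for leaving the study, so that doses received by month 7 are known for every woman analysed.
- **Confirm the supporting analysis.** State that a per-protocol result will be reported beside mITT, in women who received the doses assigned by month 7 and gave blood about one month after the month-6 dose.

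The cost is an amendment sentence with ethics board approval, a few visits that were already planned, and one further analysis of existing data. At the plan's 90% completion the per-protocol set would hold about 202 women per group.
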